### 3.5. Safety Endpoints

Safety endpoints will be summarized based on the on-treatment period unless otherwise specified.

On-treatment period is defined as the time from the first dose of study intervention through the minimum of [28 days after last dose, (start day of new anticancer therapy – 1 day)]. Anticancer therapy includes drug therapy and radiation with curative intent; the start of new anticancer therapy after the first dose of study intervention is derived as outlined in [Section 5.2.6](#). Adverse events occurring on the same day as the first dose of study intervention will be considered to have occurred during the on-treatment period. All other assessments which occur on the same day as the first dose of study intervention will be considered baseline assessments (see [Section 3.4](#) for the definition of baseline).

Safety data collected after the on-treatment period as described above will be listed but not summarized.

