7.1. Discontinuation of Study Intervention

It may be necessary for a participant to permanently discontinue study intervention. Reasons for permanent discontinuation of study intervention may include the following:

- Objective disease progression;
- Lack of efficacy (eg, increase of disease burden not qualifying as PD according to IMWG criteria)
- Global deterioration of health status requiring discontinuation;
- Unacceptable toxicity;
- Pregnancy or breastfeeding;
- Medication error without associated adverse event
- Significant protocol violation;
- Lost to follow-up;
- Participant refused further treatment;
- Withdrawal by participant;
- Investigator decision;
- Study completed;
- Study terminated by sponsor;
- Death.

Note that discontinuation of study intervention does not represent withdrawal from the study. If study intervention is permanently discontinued, the participant will remain in the study to be evaluated for safety, disease assessments, subsequent anti-cancer therapies and survival. Refer to each [sub-study protocol](#) SoA for data to be collected at the time of discontinuation of study intervention and follow-up for any further evaluations that need to be completed.

In the event of discontinuation of study intervention, it must be documented on the appropriate CRF/in the medical records whether the participant is discontinuing further receipt of study intervention or also from study procedures, post-treatment study follow-up, and/or future collection of additional information.

7.1.1. Follow-Up Visits (28/90 Days):

7.1.1.1. 28-35 Days Post-Dose

At least 28 calendar days, and no more than 35 calendar days after discontinuation of study intervention, participants will return to clinic for a safety follow-up visit, including review of concomitant treatments, vital signs, and assessment for resolution of any treatment-related AEs (refer to each [sub-study protocol](#) SoA for all activities).

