Participants continuing to experience AEs at this point following discontinuation of treatment will continue to be followed at least every 4 weeks until resolution or determination, in the clinical judgment of the investigator, that no further improvement is expected (see also [Section 8.3.1](#) for AE reporting period). If the unresolved AE is considered by the investigator as possibly related to or associated with ADA formation, the participant will be asked to return for drug concentration and ADA blood sampling at up to 3-month intervals, until the last follow-up of the AE.

7.1.1.2. 90 Days Post-Dose

The 90-day post-dose follow-up visit for AEs and contraception check may be performed via remote contact (eg, telephone). The investigator may complete these follow-up visits in clinic if any concerns are noted during the remote contact. This visit will coincide with the first long term follow up visit.

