8.3.1. Time Period and Frequency for Collecting AE and SAE Information

The time period for actively eliciting and collecting AEs and SAEs (“active collection period”) for each participant begins from the time the participant provides informed consent, which is obtained before the participant’s participation in the study (ie, before undergoing any study-related procedure and/or receiving study intervention), through and including a minimum of 90 calendar days, except as indicated in this section, after the last administration of the study intervention.

NOTE, as indicated in Section 8.3.1.2: If a participant begins a new anticancer therapy, the recording period for nonserious AEs ends at the time the new treatment is started; however, SAEs must continue to be recorded on the CRF during the above-indicated active collection period.

Only SAEs will be actively elicited and collected after completion of the active collection period described above. The SAEs will be reported to Pfizer Safety on the CT SAE Report Form only if considered reasonably related to study intervention.

Follow-up by the investigator continues throughout and after the active collection period and until the AE or SAE or its sequelae resolve or stabilize at a level acceptable to the investigator.

For participants who are screen failures, the active collection period ends when screen failure status is determined.

If the participant withdraws from the study and also withdraws consent for the collection of future information, the active collection period ends when consent is withdrawn.

If a participant permanently discontinues or temporarily discontinues study intervention because of an AE or SAE, the AE or SAE must be recorded on the CRF and the SAE reported using the CT SAE Report Form.

Investigators are not obligated to actively seek information on AEs or SAEs after the participant has concluded study participation. However, if the investigator learns of any SAE, including a death, at any time after a participant has completed the study, and he/she considers the event to be reasonably related to the study intervention, the investigator must promptly report the SAE to Pfizer using the CT SAE Report Form.

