## 1. VERSION HISTORY

This SAP for study C1071004 is based on the protocol amendment v1.0 (dated 14 February 2021).

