#### 3.5.1. Adverse Events

An adverse event is considered treatment-emergent relative to the study intervention if the event start date is during the on-treatment period (including on the date of first dose).

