### 6.7.1. Adverse Events

All analyses will be based on treatment emergent adverse events (TEAE) unless otherwise specified. Treatment emergent is defined in [Section 3.5](#). AEs not considered treatment emergent will be flagged in data listings. Summaries of TEAEs due to COVID-19 may be produced if appropriate.

A high-level summary of adverse events (all causality and treatment-related, separately) will include the number and percent of participants with:

- Any TEAE;
- Serious TEAE;
- TEAE with CTCAE Grade 3-4;
- Grade 5 TEAE;
- TEAEs leading to dose interruptions of PF-06863135;
- TEAEs leading to dose interruptions of the combination partner agent (presenting the study drug name in the summary table);
- TEAEs leading to dose reductions of PF-06863135;
- TEAEs leading to dose reductions of the combination partner agent;
- TEAEs leading to withdrawal of PF-06863135;
- TEAEs leading to withdrawal of the combination partner agent;
- TEAEs leading to withdrawal of all study drugs;
- CRS;
- ICANS.

Related TEAEs will be summarized by each individual study drug as follows:

- Related to any study drug;
- Related to PF-06863135;
- Related to the combination partner agent (presenting the study drug name in the summary table).

Seriousness, toxicity grade, action taken (interruption, reduction, and withdraw) are as reported by the investigator on the adverse event CRF.

Summaries by SOC and PT in descending order of the frequency in Phase 2 will be provided for:

- TEAEs (all causality);
- TEAEs by maximum toxicity grade (all causality);
- TEAEs (treatment-related);
- TEAEs by maximum toxicity grade (treatment-related);
- TEAEs leading to death (all causality);
- TEAEs leading to death (treatment-related);
- TEAEs leading to dose interruption of PF-06863135 (all causality);
- TEAEs leading to dose interruption of PF-06863135 (treatment-related);
- TEAEs leading to dose interruption of the combination partner agent (all causality);
- TEAEs leading to dose interruption of the combination partner agent (treatment-related);
- TEAEs leading to dose reduction of PF-06863135 (all causality);
- TEAEs leading to dose reduction of PF-06863135 (treatment-related);
- TEAEs leading to dose reduction of the combination partner agent (all causality);
- TEAEs leading to dose reduction of the combination partner agent (treatment-related);
- TEAEs leading to withdrawal of PF-06863135 (all causality);
- TEAEs leading to withdrawal of PF-06863135 (treatment-related);

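### If the supplied general SAP still governs, adverse events starting on days 29 to 90 after last dose are collected and listed but enter no AE incidence table

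*SAP*

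**What the plan says.** **General SAP, 18 March 2021.** Section 3.5: "On-treatment period is defined as the time from the first dose of study intervention through the minimum of [28 days after last dose", or the day before new anticancer therapy if earlier. It adds: "Safety data collected after the on-treatment period as described above will be listed but not summarized". Section 3.5.1: "An adverse event is considered treatment-emergent relative to the study intervention if the event start date is during the on-treatment period". Section 6.7.1: "All analyses will be based on treatment emergent adverse events (TEAE) unless otherwise specified"; events that are not treatment-emergent are flagged in listings. No AE or AESI table in 6.7.1 or 6.7.1.1 specifies otherwise. Section 3.4 takes last dose as the latest nonzero dose of any study drug. On its basis, Section 1 says: "This SAP for study C1071004 is based on the protocol amendment v1.0 (dated 14 February 2021". Section 2 lists sub-study A as the only sub-study covered.

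**Protocol (current).** Section 8.3.1 runs active collection of AEs and SAEs from consent "through and including a minimum of 90 calendar days" after the last administration. Recording of nonserious AEs stops when new anticancer therapy starts; recording of SAEs continues. Section 7.1.1.2 provides a late contact: "The 90-day post-dose follow-up visit for AEs and contraception check may be performed via remote contact".

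**Sub-study A and B SAPs.** Section 3.5 of each refers to Section 3.5 of the master SAP for the safety endpoints. Neither redefines the on-treatment period.

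**The concern.** The 28-day summary window and the 90-day collection window date from different stages of the study. Appendix 17 of the protocol records that Amendment 2 (17 June 2021, after the general SAP) lengthened the safety reporting period from 28 to 90 days, in part to catch immune-related neurological events that appear late. That log is used here only for the date and the reason. In March 2021 the two windows agreed; nothing supplied shows that the summary window was reconsidered afterwards.

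AEs are the primary endpoint of the sub-study B dose expansion (sub-study B SAP, 3.1.2) and a secondary endpoint elsewhere. If the 28-day text governs, the reported rates omit onsets in the very period that was added to find late neurological toxicity. The enrollment-hold rules in Section 7.2.1 of both sub-study SAPs state no post-dose limit. Enrollment could therefore be held for Guillain-Barré-type events that the AE incidence table shows as zero.

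**Working it through.** **1. Which onsets are tabulated, if the 28-day text governs**

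| Onset after last dose of any study drug | Collected (Protocol 8.3.1) | In AE incidence tables (general SAP 3.5, 3.5.1, 6.7.1) |
|---|---|---|
| Days 1 to 28, before new therapy | AEs and SAEs | Yes |
| Days 29 to 90, before new therapy | AEs and SAEs | No, listed only |
| Up to day 90, on or after start of new therapy | SAEs only | No, listed only |

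Days collected but not tabulated: 90 − 28 = 62, or 62/90 = 68.9% of the minimum post-dose collection period. This is a share of days, not of events.

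**2. Where late events do appear.** They are in listings. Deaths at any time are tabulated (general SAP 6.7.2). The hold rules can count them. Neuropathy symptoms reported by participants are summarized through QLQ-CIPN20. None of these is an AE incidence rate.

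**3. Size.** The documents give no rate of late-onset AEs, so the number affected cannot be computed. The cases below are illustrations. Each assumes the only qualifying event starts on days 29 to 90 without new therapy. Intervals are 95% Clopper-Pearson.

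| Setting | Tabulated | With the late event |
|---|---|---|
| Sub-study B expansion, n = 20 | 0/20 (0 to 16.8%) | 1/20 = 5.0% (0.1 to 24.9%) |
| Sub-study A Phase 2, n = 50 | 0/50 (0 to 7.1%) | 1/50 = 2.0% (0.05 to 10.65%) |

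**4. Hold rule against AE table.** For Grade 3-4 treatment-related GBS/GB-like events, the plan holds enrollment if P(rate > 3%) ≥ 0.80 under a Beta(0.5, 0.5) prior. With x events in n evaluable participants the posterior is Beta(0.5 + x, 0.5 + n − x).

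- Plan's figure reproduced: 2 events in 39 gives 0.802, and 2 in 40 gives 0.793. The band of 20-39 for 2 events is therefore right.
- 2 events in 20: Beta(2.5, 18.5), P(rate > 3%) = 0.948, so a hold is triggered.
- If both events start on days 29 to 90, the AE table shows 0/20 instead of 2/20 = 10.0% (1.2 to 31.7%).

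**5. Does the supplied general SAP govern?** The two sub-study SAPs contain 30 section pointers to the master SAP.

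- 19 match the supplied document by number and topic, including Section 3.5 (9 in sub-study A, 10 in sub-study B).
- 11 do not match (5 in sub-study A, 6 in sub-study B). All are off by exactly one section: they cite 6.5.x where the supplied document has 6.6.x, or 6.6 where it has 6.7. They include all three pointers to the safety analyses.
- Table 1 of the sub-study A SAP lists 18 March 2021 as its own version 1.
- Sub-study B was added under Amendment 4 (9 August 2021). It uses a 42-day DLT period, whereas Section 4 of the supplied general SAP gives 35 days.

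The evidence is mixed. A renumbered master SAP that was not supplied is a real possibility.

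**The case against.** The strongest objection is that the 28-day text may already be superseded. The uniform one-section shift in the 11 pointers looks like renumbering rather than error, and the supplied document does not cover sub-study B, where AEs are a primary endpoint. This stands, and the conclusion is conditional on it. Section 3.5 is nevertheless cited by both sub-study SAPs and matches by number and topic, so the window cannot be dismissed.

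A second objection is that a collection period does not dictate a treatment-emergent window, and that 28 days is a legitimate choice. That is also right. Late events remain visible in listings, and taking last dose across all study drugs lengthens the window when a partner drug continues. What is missing is a rate for the added period.

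A reader might infer more than the documents support:

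- *That the SAP contradicts the protocol.* It does not; one document governs collection and the other summary.
- *That events found at the follow-up visit are lost because of its timing* ("At least 28 calendar days, and no more than 35 calendar days after discontinuation of study intervention"). Treatment emergence depends on the start date of the event, not the visit date. An event with onset by day 28 is tabulated even if first reported at that visit.
- *That silence in the sub-study A SAP's change list shows the window was overlooked.* The window is delegated to the master SAP, so a change there need not appear in that list.
- *That limiting the dedicated AESI summaries to CRS and ICANS breaches the protocol.* Peripheral neuropathy sits in the protocol's AESI section (8.3.8), but so does lack of efficacy, and the explicit AESI label for neuropathy is only in the amendment log. Neuropathy with onset in the window enters the general AE tables, and it has its own hold tables and QLQ-CIPN20.

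**Conclusion.** The point holds conditionally. If the 28-day definition still governs, AEs starting on days 29 to 90 after last dose, and SAEs starting on or after new therapy, enter no AE incidence table even though the protocol collects them. At n = 20, a single such event is the difference between 0% and 5.0%; how many will occur is unknown. The conclusion rests on two assumptions: that the master SAP cited for Section 3.5 carries the supplied wording, and that some participants have onsets in that band. The first is less secure for sub-study B than for sub-study A. This is an inexpensive improvement to reporting. It gives no ground for saying that the plan is internally contradictory or that late events go unrecorded.

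**What to change.** 1. State which master SAP version governs each sub-study, and check the section pointers against that version. They may already be correct for it.
2. If its window is still 28 days, keep the 28-day TEAE tables. Add supplementary AE and SAE incidence tables through min(last dose + 90 days, start of new anticancer therapy − 1 day). Show SAEs starting on or after new therapy, up to day 90, in a separate table so that they do not mix with the other rates.
3. Optionally, prespecify a grouping of peripheral neuropathy, GBS/GB-like events and motor neuropathy, with incidence, grade, time to onset and time to resolution.

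The cost is some SAP wording and a few extra tables from data already collected. Laboratory, ECG and concomitant-medication outputs stay as they are. The supplementary rates will include some late disease-related events, since Protocol 10.3.2 has progression that is fatal within the active collection period reported as a Grade 5 SAE. A footnote should say so.

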#### 3.5.1. Adverse Events

An adverse event is considered treatment-emergent relative to the study intervention if the event start date is during the on-treatment period (including on the date of first dose).

#### 3.5.2. Laboratory Data

Hematology and chemistry results will be programmatically graded according to the NCI CTCAE version 5.0 for relevant parameters. A shift summary of baseline grade by maximum postbaseline grade will be presented. Parameters which cannot be graded will be summarized relative to the normal range (ie, normal range high or normal range low). Additional details are provided in [Section 6.7.3](#).

## 4. ANALYSIS SETS (POPULATIONS FOR ANALYSIS)

For purposes of analysis, the following analysis sets are defined:

Participant Analysis Set	Description
DLT-Evaluable Analysis Set	
The DLT-evaluable analysis set will include all enrolled participants who receive at least 1 dose of the study intervention in the Phase 1b part of the study and either experience DLT(s) or complete the DLT observation period without DLT. Participants without DLTs who receive less than the minimum requirement of the planned doses of each IP for reason other than treatment-related toxicity are not evaluable for DLTs.
 
The DLT observation period is 35 days from Cycle 0 Day 1 through Cycle 1 Day 28.

090177e196913362\Approved\Approved On: 19-Mar-2021 12:41 (GMT)

	
The minimum required exposure for DLT evaluability is defined as follows:
 
 
• For PF-06863135 (all sub-studies): 4 out of 5 planned doses during the DLT observation period. Participants must be able to receive the full dose on Cycle 1 Day 1 (-1/+3 dosing window) and not require any dose reductions during the DLT observation period;
 
• For nirogacestat (sub-study A): at least 75% of the planned doses and not require any dose reductions during the DLT observation period.
 

Safety Analysis Set	The safety analysis set will include all enrolled participants who received at least 1 dose of study intervention.
PK Analysis Set	
The PK analysis set will include all participants in the safety analysis set who have at least 1 post-dose concentration measurement.
 
The PK parameter analysis set will include all participants in the safety analysis set who have at least one of the PK parameters of interest for PF-06863135.

Immunogenicity Analysis Set	The immunogenicity analysis set will include all participants in the safety analysis set who have at least 1 sample tested for ADA.
Biomarker Analysis Set	
The biomarker analysis set will include all participants in the safety analysis set who have at least 1 baseline biomarker assessment.
 
Analysis sets will be defined separately for biomarkers based on blood, and bone marrow samples.

PRO Analysis Set	The PRO analysis set will include all participants in the safety analysis set who completed a baseline (last PRO assessment prior to or on the first dose of study intervention) and at least 1 post-baseline PRO assessment.

*Note:* "Enrolled" means a participant who is assigned to study intervention in IRT.

090177e196913362\Approved\Approved On: 19-Mar-2021 12:41 (GMT)

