### 2.1.1. Estimands (All Sub-studies)

#### Phase 1b

**Primary Estimand:** Dose-limiting toxicity (DLT) rate estimated based on data from DLT-evaluable participants during the DLT observation period (35 days from Cycle 0 Day 1 through Cycle 1 Day 28 ie, the 1-week period after the priming dose of PF-06863135 on Cycle 0 Day 1, plus 4 weeks of combination study intervention that begins on Cycle 1 Day 1). The estimand has the following attributes:

- Population: Relapsed/refractory multiple myeloma (RRMM) participants, as defined by the inclusion and exclusion criteria to reflect the targeted population of the treatment, who receive at least 1 dose of the study intervention in the Phase 1b part of the study and either experience DLT(s) during the DLT observation period or complete the DLT observation period without DLT. Participants without DLTs who receive less than the minimum requirement of the planned doses of each investigational product for reason other than treatment-related toxicity are not evaluable for DLTs. The minimum required exposure for DLT evaluability of PF-06863135 and the combination partner agent in the DLT observation period is specified in [Section 4](#).
- Variable: Occurrence of DLTs during the DLT observation period.
- Population-level summary measure: DLT rate defined as the number of DLT-evaluable participants with DLTs in the DLT observation period divided by the number of DLT-evaluable participants.

#### Phase 2

**Primary Estimand:** the treatment effect of PF-06863135 in combination with other partner agent on objective response rate (ORR) per the International Myeloma Working Group (IMWG) criteria as determined by investigator. The estimand has the following attributes:

- Population: RRMM participants, as defined by the inclusion and exclusion criteria to reflect the targeted population of the treatment, who received at least 1 dose of study intervention.
- Variable: Objective response defined as confirmed stringent complete response (sCR), complete response (CR), very good partial response (VGPR) and partial response (PR) per IMWG response criteria as determined by investigator, from the date of first dose until the first documentation of progressive disease (PD), death or start of new anti-cancer therapy.

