**Table 2. Study Intervention Dose Levels and Administration**

Dose Levels (DL)	Elranatamab	Nirogacestat
1 (starting dose level)	Priming Dose: 4 mg C0D1 SC Full Dose: 4 mg C1D1 SC, weekly thereafter b	100 mg PO BID continuous starting on C1D1 until response a
2	2 Step-up Priming Dose: 4 mg C0D1 SC / 8 mg C0D4 SC Full Dose: 12 mg C1D1 SC, weekly thereafter b	100 mg PO BID continuous starting on C1D1 until response a
3	2 Step-up Priming Dose: 12 mg C0D1 SC / 32 mg C0D4 SC Full Dose: 32 mg C1D1 SC, weekly thereafter b	100 mg PO BID continuous starting on C1D1 until response a
Nirogacestat De-Escalation Levels		
3A	2 Step-up Priming Dose: 12 mg C0D1 SC / 32 mg C0D4 SC Full Dose: 32 mg C1D1 SC, weekly thereafter b	100 mg PO QD continuous starting on C1D1 until response a
4A	2 Step-up Priming Dose: 12 mg C0D1 SC / 32 mg C0D4 SC Full Dose: 76 mg C1D1 SC, weekly thereafter b,c	100 mg PO QD continuous starting on C1D1 until response a
3B	2 Step-up Priming Dose: 12 mg C0D1 SC / 32 mg C0D4 SC Full Dose: 32 mg C1D1 SC, weekly thereafter b	50 mg PO QD continuous starting on C1D1 until response a
4B	2 Step-up Priming Dose: 12 mg C0D1 SC / 32 mg C0D4 SC Full Dose: 76 mg C1D1 SC, weekly thereafter b,c	50 mg PO QD continuous starting on C1D1 until response a

- a. For Dose levels 3A/3B and 4A/4B, nirogacestat will be adjusted to 50 mg QD continuous at time of confirmed VGPR. Once CR (or better) is confirmed, nirogacestat will be permanently discontinued. For all other dose levels, nirogacestat can be continued or adjusted based on this guidance, per investigator discretion. See Section 6.1.1.5.
- b. Starting at Cycle 7, if a participant has received QW dosing for at least 6 cycles and PR or better persisting for ≥2 months, dose interval will be changed from QW to Q2W. See Schedule of Activities.
- c. For participants on Dose levels 4A and 4B receiving CCI dosing, CCI the dose interval will be changed to CCI

090177e1a0f4f44c\Approved\Approved On: 14-Jun-2024 22:12 (GMT)

CCI

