### **Sample Size Estimation**

A minimum of 2-6 DLT-evaluable participants (as defined in [Section 4 in the master SAP](#)) will be treated at each dose level of elranatamab. The actual number of participants to be enrolled will depend on the number of dose levels evaluated and the number of participants treated at each dose level. Therefore, it cannot be determined in advance.

It is estimated that approximately up to 30 DLT evaluable participants will be enrolled and treated with elranatamab combination which will include at least 6 DLT evaluable participants treated at the elranatamab combination MTD level and at least 6 DLT evaluable participants at the elranatamab combination RP2D level.

If any participant is deemed non-evaluable for DLT, additional participants may be enrolled to ensure there are a sufficient number of evaluable participants in the Phase 1b of the sub-study.

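### On the supplied text, the DLT-evaluability minimum of 4 of 5 elranatamab doses fits only sub-study A dose level 1, and sub-study A's own 80% rule names no unit

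*SAP*

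**What the plan says.** **Master SAP.** The Phase 1b estimand (Section 2.1.1) describes a single priming dose followed one week later by four weeks of combination treatment. It then refers onward: "The minimum required exposure for DLT evaluability of PF-06863135 and the combination partner agent in the DLT observation period is specified in" Section 4. Section 4 sets a 35-day window and this minimum: "For PF-06863135 (all sub-studies): 4 out of 5 planned doses during the DLT observation period". It adds two conditions. One is "Participants must be able to receive the full dose on Cycle 1 Day 1 (-1/+3 dosing window"); the other is that no dose reduction is needed. Participants without a DLT who fall short "for reason other than treatment-related toxicity are not evaluable for DLTs". The only partner-drug minimum is for nirogacestat, at 75%.

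**Sub-study A SAP.** Section 4 refers to master Section 4. Table 2 has one priming dose at dose level (DL) 1 and two from DL2 upward. From DL3 these are "12 mg C0D1 SC / 32 mg C0D4 SC", and at DL4A/4B the full dose is "76 mg C1D1 SC, weekly thereafter". Section 6.1.1 cites master Section 4 and also requires at least 80% of the planned elranatamab dose. It gives a worked denominator, in mg, for nirogacestat only.

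**Sub-study B SAP.** Sections 4, 5.1.1.1 and 6.1.1 refer to master Section 4. Table 5 plans elranatamab on C0D1, C0D4 and C0D8 and then weekly from C1D1. Section 3.1.1 sets a 42-day window. The readable text gives no minimum exposure of its own.

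**Version.** Of itself the master SAP says: "This SAP for study C1071004 is based on the protocol amendment v1.0 (dated 14 February 2021").

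**The concern.** The DLT rate in this set is the Phase 1b primary endpoint, and the same data feed the Bayesian logistic regression model (BLRM) that guides dosing. One rule is declared for all sub-studies, but its count of five planned doses belongs to a regimen that most of the current dose levels no longer use.

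For a participant without a DLT who misses doses for reasons other than treatment-related toxicity, entry to the denominator then depends on which passage is applied. It also depends on whether the minimum is read as a count or a proportion and, in sub-study A, on the unit. A lenient reading admits people with little exposure as DLT-free and so pulls the observed rate down.

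A strict reading need not shrink a cohort, because in sub-study A "additional participants may be enrolled to ensure there are a sufficient number of evaluable participants in the Phase 1b of the sub-study". What is at stake is therefore an inconsistent denominator, and possibly some extra enrolment.

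**Working it through.** **Inputs.** Planned elranatamab doses from C0D1 to the end of C1, from sub-study A Table 2 and sub-study B Table 5. The calculation assumes that the printed weekly schedule holds through C1; a Table 2 footnote for DL4A/4B is partly redacted.

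**The plan's own figure.** One priming dose plus four weekly doses is 1 + 4 = 5, and 4/5 = 80.0%. This reproduces for the schedule in master Section 2.1.1 and for sub-study A DL1.

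**Planned doses and mg.**

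| Level | Doses | Planned mg |
|---|---|---|
| A DL1 | 5 | 4 + 4×4 = 20 |
| A DL2 | 6 | 4 + 8 + 4×12 = 60 |
| A DL3/3A/3B | 6 | 12 + 32 + 4×32 = 172 |
| A DL4A/4B | 6 | 12 + 32 + 4×76 = 348 |
| B, 44 mg levels | 7 | 12 + 32 + 5×44 = 264 |
| B, 76 mg levels | 7 | 12 + 32 + 5×76 = 424 |

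**Count or proportion.** As a fixed count, 4/6 = 66.7% and 4/7 = 57.1%. As a proportion, 0.80×6 = 4.8 requires 5 of 6, and 0.80×7 = 5.6 requires 6 of 7.

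**Conflict inside sub-study A, whatever the unit.** Take a participant at DL2 or above who misses two full doses other than C1D1 and so receives 4 of 6.

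- By count this is 66.7%.
- By mg it is (60−24)/60 = 60.0% at DL2, (172−64)/172 = 62.8% at DL3/3A/3B, and (348−152)/348 = 56.3% at DL4A/4B.
- All fail the 80% rule of Section 6.1.1. All pass master Section 4 if it is read as a fixed count of 4.

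**Unit in sub-study A.** One full dose other than C1D1 is missed. Retained share by mg = (planned − missed)/planned.

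| Level | By count | By mg |
|---|---|---|
| DL1 | 4/5 = 80.0% | 16/20 = 80.0% |
| DL2 | 5/6 = 83.3% | 48/60 = 80.0% |
| DL3/3A/3B | 5/6 = 83.3% | 140/172 = 81.4% |
| DL4A/4B | 5/6 = 83.3% | 272/348 = 78.2% |

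Only DL4A/4B changes status. The 80% cut there is 0.80×348 = 278.4 mg, and 278.4 − 272 = 6.4 mg short. A missed C1D1 full dose is disqualifying under master Section 4 in either unit.

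**Unit in sub-study B.** One missed full dose leaves 6/7 = 85.7% by count, and 220/264 = 83.3% or 348/424 = 82.1% by mg. The unit makes no difference there; the fixed count does.

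**Toxicity exception.** Master Section 4 excludes a shortfall only when its cause is not treatment-related toxicity. Section 6.1.1 of sub-study A states the 80% rule without that limit. On its literal wording, a DLT-free participant whose doses were missed because of treatment-related toxicity is evaluable under one passage and not under the other.

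**The case against.** **The supplied master may not govern.** It is dated 18 March 2021. The sub-study A SAP lists that same date and amendment as its own version 1, and sub-study B was first added in August 2021. Both sub-study SAPs cite master Section 6.5.1 for baseline summaries, which the supplied file has at 6.6.1. Other references do match, such as Sections 4, 5.2.6 and 5.2.10, so this is not proof. The doubt stands, and it weighs most on sub-study B.

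**Sub-study A has already set the proportion.** Section 6.1.1 is later and specific, and 80% is the same proportion as 4 of 5. This stands. The fixed-count figures matter in A only if the older general sentence is left in force beside it, which the cross-reference currently does.

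**Mg may be what is meant.** Section 6.1.1 speaks of relative dose and works its example in mg, and Section 6.6.3.1 defines elranatamab relative dose in mg for exposure summaries. A reader might infer that the DL4A/4B result is a mistake. It is not: one 76 mg dose is 76/348 = 21.8% of the plan, so failing an 80% rule in mg is simply what that rule does. The gap is that the unit is not stated for elranatamab.

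**Inferences the documents do not support.** A reader might conclude that missed doses are the only route to a shortfall, because sub-study A bars elranatamab dose reduction. Protocol Section 8.3.10 provides for errors in dosage strength, so under-dosing by error remains possible. A reader might also conclude that sub-study B has no partner-drug minimum at all. Its Section 5.1.1.1 contains redacted text, the sub-study protocols are not supplied, and a March 2021 file could not have covered lenalidomide and dexamethasone for a sub-study that did not yet exist.

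**The consequence is small.** It touches only DLT-free participants with missed doses, replacement is allowed, Phase 1b has no hypothesis test, and the model output is described as guidance. This limits the severity but does not remove the conflict.

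**Conclusion.** The point holds on the supplied text. A minimum of 4 of 5 doses in 35 days matches one regimen, sub-study A DL1, and is imported by sub-studies that plan 6 doses, or 7 over 42 days. As a fixed count it would let a DLT-free sub-study B participant with 57.1% of planned doses count as evaluable. In sub-study A it would pass 4 of 6 doses, which Section 6.1.1 fails. The remaining ambiguity in A is narrower: the unit changes the outcome for one missed full dose other than C1D1 at DL4A/4B only, 83.3% against 78.2%.

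Confidence is high on the mismatch of counts and moderate that mg is the unit intended in A. It is lower for B, where everything rests on the supplied master being the governing one. A reader might go further and infer biased escalation decisions. The documents do not allow that to be shown, because the BLRM priors are redacted. Severity is minor to should-fix.

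**What to change.** Reconcile the passages by stating the DLT-evaluable set once in each sub-study SAP, against that sub-study's own planned doses and window.

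- **Sub-study A:** keep 80%, and have the sponsor say whether it is a share of planned administrations or of planned mg. Remove or expressly supersede the 4-of-5 count. Confirm that the C1D1 condition and the treatment-related-toxicity exception still apply.
- **Sub-study B:** cite the version and date of the governing master SAP. If it is the supplied March 2021 file, replace the 4-of-5 count and the 35 days with a minimum set against 7 planned doses and 42 days, and have the sponsor state the partner-drug minimum.

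The cost is SAP wording. A few participants without a DLT may be reclassified; no new data are needed.
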